5.6 Exploring Feasibility of Individualized Coaching (post-RCT)

Participants randomized to the STEP-1 condition who did not have a \geq 6-point decrease in their ISI score⁴⁹ at 8-week follow-up data will continue on the study and receive 2 individualized coaching sessions to explore feasibility of delivering individualized coaching sessions to them (secondary aim iii). (Participants randomized to the STEP-1 condition who did have a \geq 6-point decrease in their ISI score continue on the study until the final sleep checklist measure is collected as described below, and participants assigned to the control condition end participation after week 8 data are collected). Optimal timing for the first coaching session is within 7 days after the 8-week follow-up, and the second session should be 7 days after the first. However they may be scheduled any time within 23 days after the 8-week follow-up with at least 5 days between coaching sessions. Paraprofessional coaches trained and supervised by psychologists with CBTI expertise will deliver the coaching sessions remotely by following a structured outline adapted from [name] insomnia study for young adult cancer survivors (DFCI 21-

613). During 30-minute sessions, participants will review progress and challenges in following their sleep action plan. Coaches will offer support and encouragement and may refer participants to the on-hand materials to help answer questions and reinforce program goals and suggestions. Following principles of self-care management,⁵⁰⁻⁵⁴ coaching sessions are not prescriptive, but promote survivors' self-management skills (e.g., goal-setting, problem solving) to implement their sleep action plan. At the end of the 4-week period, participants complete a questionnaire assessing acceptability and satisfaction with the coaching sessions, and will complete the ISI and Sleep Change measure. Participants will receive a \$25 gift card upon completion of this questionnaire. Administrative data on coaching session duration, and sessions missed, interrupted, or rescheduled will be collected.

5.7 OnCore Registration

As per DF/HCC SOP REGIST-101A, with the approval of the Director of the Office of Data Quality, retrospective registration will be utilized for this minimal risk study.

Institutions will register eligible participants in the Clinical Trials Management System (CTMS) OnCore as required by DF/HCC SOP REGIST-101. When required by REGIST-101, registration must occur prior to the initiation of protocol-specific procedures or assessments.

Registration requires a signed informed consent document and a completed eligibility checklist according to DF/HCC SOP REGIST-104.

Specific procedure for registering a participant in OnCore for a minimal risk study with a waiver of documentation of informed consent:

When registering a participant on OnCore, under consent form tab the “Consent for Research (1)” choose “Study Brochure,” confirming that the participant has received the approved study brochure with the elements of informed consent and has verbally consented to the study.

6.0 RISKS AND ADVERSE REACTIONS AND THEIR MANAGEMENT

Potential for some participants to experience increased daytime fatigue from the study intervention

The primary risk of this minimal risk study for participants randomized to the STEP-1 intervention is a brief (1-2 week) period of daytime fatigue, which is the result of sleep scheduling (i.e., reducing daytime sleep). Consequently, participants may experience some physical and mental side effects associated with sleepiness. However, these side effects should be similar to the effects of sleepiness they have previously experienced due to their insomnia. In order to address and mitigate this risk, the STEP-1 intervention provides information about anticipating and planning management strategies to cope with increased symptoms of fatigue that may occur. In particular, instructions will be provided to maintain personal safety by avoiding driving at times when participants are likely to become sleepy, and taking appropriate steps if they become sleepy while driving. Specifically, participants are instructed that they should immediately pull over to a safe area, stop driving and sleep if they become fatigued while driving. Additionally, participants will be provided with the contact information of the PI, [name], a licensed psychologist with extensive clinical experience with cancer survivors and insomnia treatment. Participants who have any concerns about the study are encouraged to contact him for assistance.

Potential for some participants to be disappointed with being randomized to a particular intervention

In recognition of the fact that some participants may be disappointed in the arm of the study to which they are randomized, after completing the final assessment, all participants will be offered access to the intervention they did not receive as part of the study.

Privacy and Confidentiality

We have taken steps to protect the privacy of participants during all aspects of intervention delivery and data collection.

The Zoom videoconferencing technology which will be used to conduct eligibility screening conversations and deliver the online intervention is fully HIPAA compliant. The platform is licensed to our cancer center, and is currently used for telehealth visits, research visits, educational webinars, and study meetings. As of June 2020, Zoom is encrypted using AES 256-bit GCM encryption standard, the strongest and most robust encryption standard that is currently commercially available. For additional security, our institution has locked the password function so that passwords are required for all Zoom meetings. A new individual password is created for

each session, which is then embedded into the link sent to the participant. This enables the participant to access the session securely without having to enter a password, while ensuring that only the participant has access to the meeting. Once the participant enters the meeting, the meeting will be locked which provides further protection against any other person entering the meeting either accidentally or intentionally.

The Qualtrics web-based survey platform that will be used to collect study data remotely has been used successfully by [name] for other online intervention studies. Qualtrics is the leading global provider of data collection and analysis for academic research, serving over 5,000 customers in 75 countries. The Qualtrics platform can deliver web and mobile surveys, embed videos in a larger survey, send email and mobile reminders, and automate the data collection procedures. Qualtrics provides secure collection of survey data using encrypted data transfer and complies with HIPAA protections for privacy of patient information. In our application for this study, the Qualtrics program will identify participants only by study ID, and will contain no identifiers. Participants will access the Qualtrics platform through a unique link connected only to their study ID, and email addresses will not be stored in Qualtrics, so that no protected health information is stored on the Qualtrics platform.

We will use standard IRB-approved and HIPAA compliant measures to maintain patient confidentiality, privacy and data security. Data privacy and security procedures will include: a) training staff on data sensitivity and protocols for safeguarding confidentiality; b) storing and processing sensitive hardcopy in a secured, centralized location; c) securing sensitive hardcopy in locked files when not in use; d) removing names, addresses, and other direct identifiers from hardcopy and computer readable data after they are not necessary for patient tracking and then using encrypted codes for subsequent identification of subjects; e) destroying all identifiable linkages to data after data accuracy has been verified and final analyses have been completed; f) using restricted logon identification and password protection computer protocols for all computerized entry, retrieval, and analysis.

7.0 STATISTICAL ANALYSIS

Primary Aim: *Evaluate the efficacy of the online STEP-1 intervention to improve insomnia and mood symptoms in cancer survivors.*

This is a randomized 2-arm trial comparing the STEP-1 intervention to an enhanced usual care control condition. Immediately after completing baseline assessment subjects will be randomized (1:1 by the Sealed Envelope platform) to the Experimental group which will receive the STEP-1 intervention, or the Control group which will receive the relaxation based intervention.

Randomization, with block size of 4, will be stratified by age category (40-64 years vs. 65-89 years). Primary endpoint is change in Insomnia Severity Index score from baseline to 8-weeks post-intervention. Secondary endpoint is change in mood symptoms on the Profile of Mood States-Short Form at 8-weeks. Changes in Total Sleep Time and Sleep Efficiency (calculated from the CSD-M), and Total Sleep Disturbance score from the PROMIS-SD will also be evaluated. Data analysis for these variables will follow methods used for our recently completed clinical trial of in-person insomnia interventions delivered to cancer survivors (R03CA201459). Change scores will be treated as continuous variables and primary analyses will compare the arms using 2-way analysis of variance with one between-subjects factor (STEP-1 vs. Control) and one within-subjects factor (time). Cohen's d will be used to quantify within-group effect sizes and Hedges' g adjustment will estimate between-group effect sizes. Primary and secondary endpoints are change at 8 weeks; data collected at 4-week post-assessment timepoints will be analyzed using similar methods.

Sample Size/Power: To meet our aims we require 60 participants with evaluable data, but will enroll 70 as a hedge against attrition. As is common for most CBTI interventions, STEP-1 has demonstrated large effects of $d \geq 1.00$ in our pilot testing). Using this effect size as a reference, the study is conservatively powered to detect an effect size of 0.6 (Primary Aim). With sample size of 60 (30 per arm) the study will have 90% power to detect an effect of this size (two-sided test with $\alpha = .05$). Even in the highly unlikely event that the sample size is reduced to 50 (25 per arm), the study will retain >80% power to detect an effect of this size.

Missing Data: Participants will be randomized after completing a baseline so complete baseline data are assured. Primary analysis will be an intent-to-treat analysis of randomized subjects. Based on experience using similar data collection methods (Clinical Trials document 2.5), we anticipate minimal missing data (<10%). If needed, we will use multiple imputation to account for missing data. Potential factors in the imputation model include baseline sleep and mood variables. Sensitivity analysis will impute missing change scores with values sampled from an estimated distribution of change scores from the control group participants.

Secondary Aims:

i) Explore participant and program adherence factors associated with clinically significant response to STEP-1. Logistic regression will be used to identify participant demographic and sleep factors (e.g., age, severity of insomnia symptoms) associated with a reduction of ISI scores ≥ 6 points. Variables identified in univariate analysis ($p < .10$) will be entered in a multivariable model estimating STEP-1 response from baseline variables. This analytic approach will also be used to explore how patient adherence factors (e.g., adherence to specific program strategies, number of strategies employed, consistency of adherence) are associated with a reduction of ISI scores ≥ 6 points. Depending on results of these exploratory logistic regression analyses, mediation and moderation analyses can be applied to determine how demographic and sleep variables may themselves be associated with patient adherence factors and clinically significant response to STEP-1 (i.e., reduction of ISI scores ≥ 6 points).

ii) Evaluate feasibility and acceptability of the control intervention. Descriptive statistics will be used to summarize data on duration of the control intervention sessions, as well as sessions missed, interrupted, or rescheduled. Fidelity information from the adherence checklist used to evaluate audiotapes of the control sessions will also be described using descriptive statistics. Scores on the Telehealth Usability Questionnaire, the Credibility/Expectancy Questionnaire, and a study-specific satisfaction checklist will also be summarized. While the focus will be on describing usability and acceptability of the control intervention, comparisons between the control and STEP-1 sessions on these metrics will also be explored using parametric (e.g., t-test) and non-parametric methods (e.g., chi-square, Mann-Whitney).

iii) Explore feasibility of delivering individualized coaching sessions for participants who do not have a significant response to the STEP-1 intervention. Similar to methods used for secondary aim ii, descriptive statistics will be used to summarize data on duration of the coaching sessions, as well as sessions missed, interrupted, or rescheduled. Fidelity information from the coaches' self-report checklists and the adherence checklist used to evaluate audiotapes coaching sessions will also be summarized and descriptive statistics reported, as will participants questionnaires reporting their perceived acceptability and satisfaction with the coaching sessions.

iv) Describe participants' satisfaction with the STEP-1 program and their suggestions for improving it. Similar to methods used for secondary aims ii & iii, descriptive statistics will be

used to summarize data from the final program satisfaction questionnaire. The measurement properties of the rating scale items will be explored for consistency and reliability (e.g., item-scale correlations, alpha with item deleted) and summarized in a total satisfaction score as appropriate. Closed-ended items asking participants to rate usefulness of STEP-1 program elements will be summarized. To explore how participants' ratings of usefulness may be associated with their treatment response, the difference in these ratings between participants with and without a reduction of ISI scores ≥ 6 points between baseline and week-8 will be explored using non-parametric statistics (e.g., Mann-Whitney). Finally, closed- and open-ended items capturing participants' report of additional program elements that would improve the STEP-1 program will be summarized.

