4.0 RECRUITMENT

This study will follow procedures currently in place for other survivorship interventions at DFCI (17-515, 17-402) in order to identify potentially eligible survivors for recruitment purposes. These procedures have been developed in consultation with the disease centers and have proven to be effective and non-burdensome for clinicians and patients, while ensuring that only survivors appropriate for recruitment are approached. Study investigators will collaborate with clinicians in the clinics at Dana-Farber Cancer Institute in order to identify and recruit eligible survivors followed in these clinics. Recruitment materials and a study information sheet can be found in Appendix A. After getting permission to approach the subject from their oncology/survivorship provider, subjects will be approached, screened for eligibility, and recruited by a member of the study staff. While this could occur in person at scheduled clinic visit, as many survivorship visits are currently conducted as telehealth visits, it is anticipated that most survivors will be contacted by telephone, videoconference, email, or mail. These potential participants will receive the Study Information Sheet by email or mail. Templates for all of these recruitment methods can be found in Appendix A.

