5.2 Methods

See section 5.5 for descriptions of all study measures. Copies of the assessments can be found in Appendix B, and participant correspondence in Appendix C.

Informed Consent: We are requesting a Waiver of Documentation of Informed Consent for this study, as it is a minimal risk study involving no procedures (questionnaires and educational session) for which signed consent is generally required outside of the research context. The intervention sessions in this study are similar to educational sessions currently conducted through the Blum Center at DFCI, and for which no signed consent is required. A similar online intervention currently being conducted by [name] (17-515) was granted a waiver of documentation of consent, and we propose to utilize those approved consent procedures for this study. Potential participants will be provided with a study information sheet which contains all the elements of informed consent (See Appendix A), and will have a consent conversation with a member of the study staff in which they can ask questions about the study or study procedures before providing verbal consent. As it is anticipated that many survivors will not have in person clinic visits at DFCI for the foreseeable future, it is expected that most of these consent versions will take place by telephone or videoconference, although they could be in person if requested.

Intervention session: After expressing interest in participating, participants will be scheduled for an individual videoconference intervention session. The intervention session consists of the following components:

1) Informed Consent: Study staff will review the study procedures and the Study Information Sheet with the participant and answer any questions they may have. They will then obtain verbal consent. (Verbal consent procedures can be found in Appendix A)

2) Baseline measures: Study staff guide participants in completing baseline measures including insomnia and mood using the Qualtrics web-based survey platform.²⁹ The participant will also schedule their 4-week follow-up phone appointment with study staff at this time. Additionally, participants will be asked to provider preferences for all future contact and correspondence (i.e., phone, email, send secure, text, mail) and these preferences and addresses/phone numbers will be recorded in the participant's record.

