3) Randomization: Once baseline measures are completed, randomization will be performed using Sealed Envelope, a commercially available online software application for randomising patients into clinical trials. Participants will be randomized (1:1) to either: **1)** STEP-1, or **2)** an enhanced usual care control condition. No identifiable information or PHI is entered into Sealed Envelope; participants are identified only by a study team generated ID number.

4) Intervention Delivery. Once randomized, the participant will immediately receive their assigned intervention session via videoconference. (See sections 5.3 and 5.4 for descriptions of the interventions).

5) Session evaluation: Participants will receive a link to a questionnaire on which they will report on ease of use and acceptability, satisfaction, and credibility of the session. To promote completion of the questionnaire, participants will be encouraged to complete it while still in the Zoom session, but can choose to complete it at a later time. Participants will receive a \$10 gift card upon completion of this evaluation.

Post-intervention Follow-up: At 4 and 8 weeks post-intervention, study staff will recontact participants by telephone at previously scheduled times, ask them to enter follow-up data directly into Qualtrics, and provide technical assistance if needed. Participants who cannot complete the full assessment at that time due to time constraints or logistical barriers will be asked to complete the 7-item ISI (primary outcome measure) verbally and their responses will be collected; they will then be asked to complete the full questionnaire at their earliest convenience. Participants will receive emailed reminders in advance of each phone call. At the 4-week call, participants will schedule a phone call for the next follow-up assessment.

Incentive: Participants will receive a \$25 Amazon gift card upon completion of each follow-up assessment.

Optional 8-week-post ISI: At the time of their final follow-up phone call, participants will be asked if they would be willing to complete an additional sleep checklist two months later. Participants who agree will receive a Qualtrics link to the 7-item ISI 8 weeks later by email. This would take approximately 1-2 minutes to complete, and participants will not receive an incentive for this optional checklist. The link would be sent again a week later for non-responders, but participants will receive no additional reminders.

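### A single published block size of 4, with no staff blinding or role separation described, could let the team deduce up to about 22 of 70 allocations before consent and baseline

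*Combined protocol and SAP*

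**What the plan says.** **Randomisation scheme.** Section 7.0: "Randomization, with block size of 4, will be stratified by age category (40-64 years vs. 65-89 years". Section 5.2 gives the ratio ("Participants will be randomized (1:1) to either" STEP-1 or control) and the system: "randomization will be performed using Sealed Envelope, a commercially available online software application for randomising patients into clinical trials". On numbers, section 7.0 says the study "will enroll 70 as a hedge against attrition".

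**Order of events and who acts.**
- Recruitment (section 4.0): "subjects will be approached, screened for eligibility, and recruited by a member of the study staff".
- Consent, first step of the session (section 5.2): "Study staff will review the study procedures and the Study Information Sheet with the participant and answer any questions they may have".
- Baseline, second step (section 5.2): "Study staff guide participants in completing baseline measures including insomnia and mood using the Qualtrics web-based survey platform".
- Delivery, directly after randomisation (section 5.2): "Once randomized, the participant will immediately receive their assigned intervention session via videoconference".

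STEP-1 is given one to one by a trained presenter (section 5.3), and the control session is given individually by a member of the study team (section 5.4). Age is an eligibility item (section 3.1), so the stratum is known at screening.

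The document does not say who operates Sealed Envelope, or whether the person who takes consent and guides baseline also delivers sessions or knows earlier allocations.

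**The concern.** Taking consent and baseline before randomisation protects a trial only if the next allocation cannot be predicted at that moment. With one known block size and two strata that are known in advance, the run of past allocations sometimes fixes the next one. The team delivers both arms live, so past allocations are visible within the team.

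Foreknowledge could affect who is booked next, how consent is discussed, and how completion of the baseline ISI is guided. The last matters because the primary endpoint is change in ISI from baseline. Section 7.0 compares the arms by a group-by-time analysis of variance with no stated baseline covariate, so any shift in the baseline score enters the change score in full. Bias of this kind is hard to detect or correct afterwards.

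**Working it through.** The plan gives no predictability figure, so there is none to reproduce.

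**Inputs.** Block size 4, two age strata and 70 enrolled (section 7.0); 1:1 ratio (sections 5.2 and 7.0). Each block holds 2 STEP-1 and 2 control places, giving 6 equally likely orders. *Assumption:* the observer knows the block size and every earlier allocation in the stratum.

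**Step 1: certain allocations in a block of 4.** Positions 1 and 2 are never certain. Position 3 is certain when the first two match (2 of 6 orders, 1/3). Position 4 is always certain.

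Share certain = (0 + 0 + 1/3 + 1)/4 = 1/3 = 33.3%.

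**Step 2: 70 participants.** The stratum split is not given. With 35 per stratum (assumption) there are 8 full blocks and 3 further places:
- per stratum: 8 × 4/3 + 1/3 = 11
- in total: 22 of 70 = 31.4%

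Over all possible splits the expected number runs from 22.0 to 22.7 (31.4% to 32.4%).

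**Step 3: best-guess hit rate.** The best guess is the arm with fewer allocations so far. It is right with probability 1/2, 2/3, 2/3 and 1 at the four positions, a mean of 0.708. With 35 per stratum: (8 × 2.833 + 1.833)/35 = 0.70. Chance is 0.50.

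**Step 4: varying block sizes.** These are simulated with 35 per stratum and an observer who knows the set of sizes but not their order.

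| Block sizes | Certain | Best guess correct |
|---|---|---|
| 4 only | 31% (about 22 of 70) | 70% |
| 4 and 6 | about 6% (about 4 of 70) | about 68% |
| 4, 6 and 8 | about 2% (fewer than 2 of 70) | 67% |

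The best guess needs only the running tally in the stratum, because every block ends in balance. In simulation, an observer with the tally but no knowledge of the sizes had the same hit rate (67.3% for 4, 6 and 8). Withholding the sizes therefore prevents certainty; it does not lower the hit rate of someone who keeps a tally.

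**Step 5: illustration of bias.** *Assumption with no support in the document:* foreknowledge shifts ISI change by 0.5 to 2 points in the expected direction in each arm.
- Staff act only on certain allocations: bias = 2 × share certain × shift. Fixed 4: 2 × 0.314 × (0.5 to 2) = 0.3 to 1.3 points. Sizes 4, 6 and 8: 2 × 0.022 × (0.5 to 2) = 0.02 to 0.09 points. (Simulation runs gave shares of 0.022 to 0.025.)
- Staff act on every best guess: bias = 2 × (2p − 1) × shift, where p is the hit rate. Fixed 4 (p = 0.70): 0.40 to 1.60 points. Sizes 4, 6 and 8 (p = 0.673): 0.35 to 1.38 points, about 14% lower.

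**Step 6: cost in balance.** An unfinished block can leave a stratum out of balance by at most half the block: 2 for size 4, 4 for size 8. If both strata were off by 4 in the same direction, the arms would be 39 and 31. Efficiency relative to 35 and 35 is then 4 × 39 × 31/70² = 0.987. The corresponding worst case for size 4 is 37 and 33, or 0.997.

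**The case against.** **Staffing is not described closely enough to say who knows what.** A reader might infer that nobody is blinded and that the same people book, consent, guide baseline, randomise and deliver. The document does not say so. It refers to study staff, a trained presenter and a study team member, and leaves open whether these are one person or several. It also does not name who operates the randomisation system. This stands: the figure of about one third is a ceiling that requires someone to follow every earlier allocation in the stratum.

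**The routes to harm are narrow.** Eligibility rests on fixed self-report criteria, including an ISI threshold applied at screening. The baseline ISI is self-reported in Qualtrics; staff guide completion, and nothing says they rate it. Sessions are booked ahead, and certainty attaches only to the next person actually randomised in a stratum. This limits the likely size but leaves approach, scheduling, the tone of consent and guidance at baseline.

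**A central service is used.** Sealed Envelope hides the list. It does not prevent deduction from past allocations when the block size is known.

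**Varying the blocks barely changes guessing.** This also stands. A reader might infer from the certainty-only figures that the fix cuts bias more than tenfold. That holds only if staff ignore strong hunches; if they act on best guesses the reduction is about 14%.

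**Conclusion.** The concern holds as an avoidable weakness in allocation concealment. With one published block size of 4 in two strata, up to 31% to 33% of allocations, about 22 of 70, can be known before consent and baseline. This assumes that someone with access to the next participant tracks past allocations by stratum. The arithmetic is exact. The staffing premise is an assumption that the document neither confirms nor excludes.

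Nothing in the document shows that foreknowledge is used or that the result is biased. The bias ranges depend on an assumed shift and on which model of behaviour applies, so neither should be quoted alone. The case for change is that certainty can be nearly eliminated at little cost, and the plan gives no reason for a fixed, published block size. It is worth correcting but does not invalidate the trial.

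**What to change.** Set Sealed Envelope to randomly varying block sizes (for example 4, 6 and 8) within the two age strata. In section 7.0, replace the block-size clause with: *with randomly varying block sizes, not disclosed to staff who recruit, take baseline measures or deliver sessions*. If randomisation has begun, apply this to the blocks that remain.

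Non-disclosure is part of the fix, because the remaining 2% or so of certain allocations arises only for someone who knows the sizes. It does not stop guessing from a running tally. Section 5.2 should therefore also state who takes consent, guides baseline, operates the randomisation and delivers sessions, and whether those who see participants before randomisation have access to past allocations.

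The cost is one platform setting and a short protocol edit, with some extra handling if the trial is under way. The possible end-of-trial imbalance rises from 2 to 4 per stratum. Even in the worst case this costs about 1% in efficiency, which is negligible for power.
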